8.3.2. Handling of Expedited Safety Reports

advanceCOR will notify Principal Investigators of all SAEs that are suspected (related to the investigational product) and unexpected (i.e. not previously described in the Investigator Brochure). In the European Union (EU), an event meeting these criteria is termed a Suspected, Unexpected Serious Adverse Reaction (SUSAR). Investigator notification of these events will be in the form of an expedited safety report (ESR).

Other important findings which may be reported by the sponsor as an ESR include: increased frequency of a clinically significant expected SAE, an SAE considered associated with study procedures that could modify the conduct of the study, lack of efficacy that poses significant hazard to study subjects, clinically significant safety finding from a nonclinical (e.g. animal) study, important safety recommendations from a study data safety monitoring board, or sponsor decision to end or temporarily halt a clinical study for safety reasons.

Upon receiving an ESR from advanceCOR, the Principal Investigator must review and retain the ESR with the Investigator Brochure. Where required by local regulations or when there is a central IEC for the study, the sponsor will submit the ESR to the appropriate IEC. The Principal Investigator and IEC will determine if the informed consent requires revision. The Investigator should also comply with the IEC procedures for reporting any other safety information.

8.3.3. Non-serious Adverse Events

The collection of nonserious AE information should begin at initiation of study participation, i.e. from the timepoint of obtaining informed consent. Nonserious AE information should also be collected from the start of a placebo lead-in period or other observational period intended to establish a baseline status for the subjects.

If an ongoing nonserious AE worsens in its intensity or its relationship to the investigational product changes, a new nonserious AE entry for the event should be completed. Nonserious AEs should be followed to resolution or stabilisation, or reported as SAEs if they become serious (see Section 8.3.1). Follow-up is also required for nonserious AEs that cause interruption or discontinuation of investigational product, or those that are present at the end of study participation. Subjects with nonserious AEs at study completion should receive post-treatment follow-up as appropriate. If no follow-up report is being provided, the Investigator must provide a justification.

All identified nonserious AEs must be recorded and described on the appropriate nonserious AE page of the CRF.

8.4. Laboratory Test Abnormalities

All laboratory test abnormalities captured as part of the study should be recorded on the appropriate pages of the CRF, or be submitted electronically from a central laboratory. In addition, the following laboratory abnormalities should also be captured on the nonserious AE CRF page or SAE paper CRF page as appropriate:

- Any laboratory test result that is clinically significant or meets the definition of an SAE
- Any laboratory abnormality that required the subject to have the investigational product discontinued or interrupted
- Any laboratory abnormality that required the subject to receive specific corrective therapy

It is expected that wherever possible, the clinical, rather than the laboratory term would be used by the reporting Investigator (e.g. anaemia versus low haemoglobin value).

8.5. Overdose

An overdose is defined as the accidental or intentional ingestion or infusion of any dose of a product that is considered both excessive and medically important. All occurrences of overdose must be reported as an SAE.

8.6. Pregnancy

Sexually active WOCBP must use an effective method of birth control during the course of the study, in a manner such that risk of failure is minimised.

8.6.1. Requirements for Pregnancy Testing

All WOCBP MUST have a negative pregnancy test within 72 hours prior to receiving the investigational product. The minimum sensitivity of the pregnancy test must be 25 IU/L or equivalent units of HCG. If the pregnancy test is positive, the subject must not receive the investigational product and must not continue in the study.

Pregnancy testing must also be performed throughout the study as specified the flow chart/time and events schedule (page 24) and the results of all pregnancy tests (positive or negative) recorded on the CRF or transferred electronically.

In addition, all WOCBP should be instructed to contact the Investigator immediately if they suspect they might be pregnant (e.g., missed or late menstrual period) at any time during study participation.

8.6.2. Reporting of Pregnancy

If, following initiation of the investigational product, it is subsequently discovered that a study subject is pregnant or may have been pregnant at the time of investigational product exposure, the Investigator must immediately notify advanceCOR of this event and record the pregnancy on the Pregnancy Report Form (not an SAE form). Initial information on a pregnancy must be reported immediately to advanceCOR and the outcome information provided once the outcome is known. Completed Pregnancy Report Forms must be forwarded to advanceCOR according to SAE reporting procedures described in Section 8.3.1.

Protocol-required procedures for study discontinuation and follow-up must be performed on the subject unless contraindicated by pregnancy (e.g. x-ray studies). Other appropriate pregnancy follow-up procedures should be considered if indicated. Follow-up information regarding the course of the pregnancy, including perinatal and neonatal outcome must be reported.

Any pregnancy that occurs in a female partner of a male study participant should be also reported to advanceCOR.

8.7. Other Safety Considerations

Any significant worsening noted during interim or final physical examinations and any other potential safety assessments, whether or not these procedures are required by the protocol, should also be recorded on the appropriate nonserious AE page of the CRF or SAE paper CRF page.

Classification of cause specific mortality will be performed according to the guidelines listed in Appendix B.

In addition to the regular SAE reporting requirements described in section 8.3.1, any death of any patient randomised into the study must be reported by the Principal Investigator to the Regulatory authority, leading ethics committee as well as the local ethics committee of the study site at which the patient was enrolled as soon as possible.

9. STATISTICAL CONSIDERATIONS

9.1.1. Endpoint Analysis

Endpoint analysis will be performed when 150 patients have completed visit 5 or when advised by the DSMB, whichever occurs earlier. Endpoint analysis includes all data generated from visits 1 to 3.

9.1.2. Additional Analyses

Additional analysis will be performed after the trial has been completed i.e. when the last patient has completed visit 5 or when advised by the DSMB. Additional analyses include all data generated from visit 1-7.

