7.1.5. Visit 5: 24 hrs after CEA or other intervention (\pm 24 hrs)

- Physical examination/ vital signs
- Review of concomitant medication
- Assessment of AEs including wound healing complications
- Assessment of clinical outcome
- ECG examination
- Assessment of interventional outcome and NIHSS
- Cerebral DWI-NMR post intervention (12-72 hrs after intervention)
- clinical biochemistry, clinical haematology (incl. assessment of bleeding according to RE-LY study group criteria), coagulation and urinalysis

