7.1.7. Visit 7: 12 months telephone follow up (\pm 1 month)

- Assessment of clinical outcome

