9.2.3. Database Lock

The database will be only locked after the following requirements are fulfilled:

- All data have been entered in the database
- Decisions on how individual protocol violations are to be dealt with have been agreed upon
- Written authorisation from the project leader of trial at advanceCOR GmbH has

been granted

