Data management based on GCP refers to the activities defined to achieve safe routines to enter Subject information into a database, efficiently and avoiding errors. The data management routines include procedures for handling of CRFs, database set-up and management, data entry and verification, data validation of database and documentation of the performed activities including information of discrepancies in the process.

The database, the data entry screens and program will be designed in accordance with the study protocol and the CRF. Data recorded in the CRFs and electronically saved data sent from the central laboratories will be entered/ transmitted into the database at d.s.h.

statistical services GmbH and computerised logical checks will be used to ensure the quality of the data (e.g. double data entry). Errors found in the data will be issued on Data Query Forms (DQFs) by d.s.h. statistical services GmbH and the DQFs or queries will then be returned to the study site for resolution. The database will be updated according to the query resolutions and the DQFs will then be archived with the corresponding CRF.

The database will be locked when clean file has been declared. Any changes to the database after that time can only be made by joint written agreement between the Sponsor, the Study Statistician, the Study Data Manager. The breaking of the code will take place after clean file.

The computerised data processing will be the responsibility of d.s.h. statistical services GmbH. Data will be processed in agreement with local legislations.

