### **7.2 Protocol Deviations and Violations/Data Review**

After all queries issued and answered to the extent possible, all medical codes are approved, all SAEs are reconciled, and prior to locking and unblinding the database, a Data Review Meeting will be held. The primary purpose of the meeting will be to resolve outstanding data issues, to examine protocol deviations, to define the analysis sets, and to finalize other statistically related issues.

At the Blinded Data Review Meeting, possible protocol violations will be classified as “major”, “minor”, or “not a protocol violation”. Subjects will be allocated to the individual data sets with regard to the classification of possible protocol violations. The final data sets shall be described in detail in the Blinded Data Review Report.

Major protocol deviations - leading to exclusion from the PP population - are - but not limited to - any of the following conditions:

- Patient did not receive the study medication as planned
- Oral anticoagulation or dual anti-platelet therapy within aspirin or clopidogrel and other P2Y inhibitors at screening (3 days for dipyridamole extended release; 8 hours for tirofiban/Aggrastat)
- Other concomitant medication prohibited according to the exclusion / inclusion criteria
- Systolic blood pressure >190 mmHg
- Cardiac cause of embolisation (atrial fibrillation or other cardiac cause e.g. artificial heart valves)

Definitions of protocol deviations checked by program are summarized in the following table. This table also includes proposals for classifying protocol deviations as “major”, which are referred to as protocol violations. These should be seriously considered and discussed during the

data review meeting with regard to their impact on statistical analysis and the validity of the results, and the definition of subject populations.

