## **8. STATISTICAL ANALYSIS**

### **8.1 Disposition of Subjects and Withdrawals**

Patients without any documented application of any study medication (without any documented infusion) will be excluded from all statistical analyses, but will be displayed in all data listings.

- The disposition of patients with regard to
  - enrolment of 1st patient and last follow-up of last patient
  - the number of patients enrolled (=subjects who gave informed consent),
  - number of study centres
  - number of enrolled patients by study centre
  - the number and percent of patients who discontinued prematurely within the study period,
  - the number and percent of patients who completed the study by treatment group and study centres.

will be summarised by means of frequency tables.

- For patients with a premature discontinuation the frequency of reason for discontinuation due to
  - AE
  - SAE
  - Withdrawal of consent
  - Investigator decision
  - Death
  - Termination criterion arose: Specification
  - other

will be summarised by treatment group and study centres.

In addition, all treated patients who discontinued prematurely from the study treatment and/or the study (according to the corresponding CRFs) will be listed; at least the time-point of discontinuation and the main reason for discontinuation.

- Analysis population

Inclusion/Exclusion criteria will be listed in the individual listing of raw data

Adherence to the protocol will be described by

- number and percent of patients with at least one deviation from the protocol
- number and percent of patients with at least one major deviation from protocol
- number and percent of patients with major deviations from protocol by type of protocol deviation
- number and percent of patients adhering to each analysis population

using frequency tables

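### Protocol 9.1.2 triggers a Visit 1–7 analysis at the last patient's Visit 5, before Visits 6 and 7 are due; a separate, lesser point is that 9.3 dates treatment-emergent events from screening

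*Protocol*

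**What the plan says.** **Timing of the analyses.** Protocol 9.1.1 covers Visits 1 to 3: "Endpoint analysis will be performed when 150 patients have completed visit 5", or earlier on the DSMB's advice. Protocol 9.1.2 covers everything else. It equates completion of the trial with the point "when the last patient has completed visit 5 or when advised by the DSMB. Additional analyses include all data generated from visit 1-7". The last scheduled contact is in Protocol 7.1.7, "Visit 7: 12 months telephone follow up", with a window of one month either side. SAP section 1 mentions an interim and/or a final analysis and gives a trigger for neither. SAP 8.4.5 compares cumulative clinical endpoints at 3 and 12 months.

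**Treatment-emergent events.** Protocol 9.3 (Safety) restricts the analysis to treatment-emergent events, defines these as events that started or got worse after Visit 1, and compares groups by Pearson's chi-squared test. The only exposure is the single infusion at Visit 2 (7.1.2). Serious and non-serious events are both collected from consent (8.3.1, 8.3.3). SAP 8.5.4 tabulates adverse events without an onset rule, and SAP 8.5 says that safety outcomes will be compared between groups.

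**The concern.** The 9.1.2 trigger falls within days of the last infusion, while its stated scope runs to a telephone call a year later. An analyst who follows the sentence literally would run the additional analysis with the later follow-up of recently treated patients still outstanding. The 3- and 12-month rates of death, stroke/TIA and myocardial infarction would then mix patients with full follow-up and patients without it. The plan has no rule for the second group and does not ask for the number followed.

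The second rule is a separate matter. An event between screening and infusion cannot have been caused by the study drug. Under 9.3 it is nevertheless labelled treatment-emergent and enters the between-group comparison, provided that the patient was later dosed.

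**Working it through.** The plan states no figure to reproduce, so the check is visit-window arithmetic, with 1 month = 365.25/12 = 30.44 days and T = day of infusion.

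**Part 1: can the trigger deliver the scope?**

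- Visit 4 (7.1.4) is at T + 3 days, −69 h/+5 days. The latest date is T + 8 days.
- Visit 5 (7.1.5) is 24 h ± 24 h after the intervention. Nominal: 3 + 1 = T + 4 days. Latest: 8 + 2 = T + 10 days.
- The Visit 5 scan has its own window, "Cerebral DWI-NMR post intervention (12-72 hrs after intervention"). Latest: 8 + 3 = T + 11 days.
- Visit 6 (7.1.6) is at 3 ± 1 months. Earliest: 2 × 30.44 = T + 60.9 days.
- Visit 7 (7.1.7) is at 12 ± 1 months. Earliest: 11 × 30.44 = T + 334.8 days.

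Gap for the last patient = date of the later visit − date of Visit 5:

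| Case | To Visit 6 | To Visit 7 |
|---|---|---|
| Smallest, scan at T + 11 days | 60.9 − 11 = 49.9 days | 334.8 − 11 = 323.8 days |
| Smallest, Visit 5 at T + 10 days | 60.9 − 10 = 50.9 days | 334.8 − 10 = 324.8 days |
| Nominal, Visit 5 at T + 4 days | 91.3 − 4 = 87.3 days | 365.25 − 4 = 361.3 days |

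No combination of windows brings Visit 6 or Visit 7 forward to the trigger. If 150 patients are enrolled, 9.1.1 and 9.1.2 also fire on the same event, so the wider analysis has no timing of its own.

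What is exposed: outcomes that need Visit 6 or 7. What is not exposed: the microembolic signal endpoints, which end at Visit 3, and the Visit 5 imaging endpoints once the last scan is done.

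How many patients would be affected depends on how many were treated in the months before the trigger. The documents give neither an accrual curve nor a last treatment date, so no count can be derived.

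**Part 2: what do pre-infusion events do?**

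Let p₀ be the share of patients in each arm with an event between screening and infusion, and p₁ and p₂ the post-infusion risks in two arms. Assume that p₀ is the same in both arms, as randomisation gives in expectation, and that events in the two periods are independent.

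- Observed risk in arm i = p₀ + (1 − p₀)pᵢ
- Observed difference = (1 − p₀)(p₂ − p₁)

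The difference shrinks by the factor 1 − p₀ and does not change sign. The documents give no value for p₀. As an illustration only, with assumed values p₀ = 2%, p₁ = 10%, p₂ = 30% and 50 per arm:

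- Observed risks: 0.02 + 0.98 × 0.10 = 11.8% and 0.02 + 0.98 × 0.30 = 31.4%
- Difference: 19.6 points instead of 20.0
- 95% half-width: 1.96 × √(0.118 × 0.882/50 + 0.314 × 0.686/50) = 15.7 points

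In this example the dilution is 0.4 points, far below the sampling error.

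**The case against.** **Trigger.** The best defence is that the mention of Visit 5 is a slip that other text contains. Section 9.1.2 itself places the analysis after the trial is complete and names Visits 1 to 7. Protocol 9.2.1 releases records for evaluation only after lock, and 9.2.3 makes lock conditional: "All data have been entered in the database". Protocol 10.6 adds "The breaking of the code will take place after clean file", and SAP 7.2 says that "prior to locking and unblinding the database, a Data Review Meeting will be held". SAP 8.1 will report "enrolment of 1st patient and last follow-up of last patient". This stands as evidence of intent. It does not settle the matter, because none of these passages makes Visit 7 a condition, and all data entered can be read as all data due so far. The DSMB alternative is a second route to the analysis and leaves the conflict in place.

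A reader might infer that a sizeable, quantifiable share of patients will lack 12-month data. The documents do not support that. Any percentage would rest on an invented accrual pattern, and the SAP, dated 10.06.2019, describes recruitment as past.

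**Treatment-emergent rule.** The protocol states its definition openly, and the SAP uses Visit 1 as baseline for vital signs and ECG. The interval is probably short: Visit 1 procedures take place within 24 hours (7.1.1), and the synopsis gives about 6 days per subject against a nominal Visit 5 at T + 4 days, which suggests about 2 days from screening to infusion. That is an inference, since no maximum interval is stated. The schedule starts adverse event assessment at Visit 2, and 8.3 places the general prompt at visits after treatment. These points stand and make the effect small. The safety set does not remove it, because it excludes undosed patients and not earlier events in dosed patients.

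A reader might infer that the rule favours one arm or hides harm. It does neither systematically: pre-infusion events are balanced in expectation. SAP 7.6 treats safety data as descriptive, so no formal decision turns on them. The count of drug-related events should also be unaffected, because 8.2 assigns no relationship when no product was taken.

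**Conclusion.** Part 1 holds as an error in the wording of 9.1.2. The contradiction follows from the visit windows alone and needs no outside assumption: at the stated trigger the last patient is at least about 50 days short of Visit 6 and about 324 days short of Visit 7. The consequence is conditional. The 3- and 12-month rates are incomplete only if the sentence is followed literally. The surrounding text suggests that this was not intended, and the actual loss may be nil. The number of patients affected cannot be computed.

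Part 2 holds as a separate and lesser point. The 9.3 definition takes the wrong starting point for a single-infusion trial, and the SAP does not correct it. The effect is mislabelling and slight, non-directional dilution of a descriptive comparison. Its size cannot be computed from the documents.

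**What to change.** **Part 1**

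- Protocol 9.1.2: change the trigger to the last patient's Visit 7, or that patient's documented death, withdrawal or loss to follow-up.
- SAP section 1: state the trigger and the visits covered for each analysis it names.
- SAP 8.4.5: print the number of patients followed at 3 and at 12 months beside each rate. This also protects the tables if the DSMB route is used.

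The cost is that the additional analysis waits for a telephone call that is already scheduled. If that follow-up is already complete, only the wording changes.

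**Part 2**

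- Protocol 9.3 and SAP 8.5.4: define treatment-emergent as beginning or worsening after the start of infusion, and list earlier events separately.
- Because 8.2 asks for the date of onset and not the time, add a convention for events that start on the day of infusion.

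No new data are needed: 7.1.2 already requires the time of administration, and onset is already recorded for every event. SAP section 1 allows changes short of a major one to be documented in the SAP and the study report.

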9.2. Data Management

9.2.1. Data Handling and Quality Control

Data management and data quality assurance will be performed in compliance with international guidelines (GCP, ICH) and SOPs and working instructions of d.s.h. statistical services effective at that moment in time.

d.s.h. statistical services will document receipt of completed CRFs and perform a general check for legibility, completeness of pages, mandatory values, dates and signatures of Investigators. Subsequently, independent personnel will enter trial data into a validated database system (double data entry) during which incorrect data types and values out of defined ranges will be detected. Changes made in valid data or system operations will be documented by audit trail. Following double data entry, first and second entries will be reconciled using the SAS Compare procedure (data verification).

Data will be checked for plausibility and consistency. Automatic and manual checks required to identify discrepancies will be described in a Data Cleaning Plan. All identified discrepancies are reviewed by data management personnel. Discrepancies can be resolved internally by inspection of the CRF and related data (e.g. if caused by data entry) or by producing Data Query Forms (DQFs) to be sent to the Investigator's site(s) for resolution. Once these queries are resolved and corrections have been implemented in the database, verification and validation procedures will be repeated until no further queries remain. Subsequently, a 10% quality control audit is performed. For this purpose, a computer program randomly selects 10% of the patients from the database for complete data comparison with the original CRFs.

Furthermore, 100 % of all patients' key data (i.e. adverse events) will be checked and formal quality control will be performed according to d.s.h. statistical services' SOP DM09. Once all Data Quality Control steps are completed and written authorisation of the project leader, data manager and statistician is obtained, the database is locked and records are released for reporting and statistical evaluation

